4.0 THERAPEUTIC PROGRAM

This phase III study will randomize eligible patients with cervical, endometrial or vaginal cancer undergoing chemoradiation therapy (see above for eligibility criteria) to receive either 34.3 mg of granisetron formulated in a transdermal patch (Sancuso) replaced every 7 days (Group A) **OR** 8 mg of ondansetron orally thrice daily starting with cisplatin administration and continued for 72 hours after chemotherapy infusion (Group B). Patients may not be enrolled on study if they have already started their chemotherapy treatment or have received more than 7 days of radiation prior to starting their chemotherapy.

In addition, data on compliance/ease of administration, amount of nausea and vomiting, and effect of nausea and vomiting on quality of life will also be collected. These data will be collected weekly via self-administered questionnaires that are estimated to take < 5 minutes to complete.

Study Drug and Dosage Schedule

Group A: 34.3 mg of granisetron formulated in a transdermal patch (Sancuso) replaced every 7 days. Patients will have the transdermal patch placed/replaced prior to the IV infusion of cisplatin. At cycle 1, patients will receive IV ondansetron 8mg prior to IV cisplatin. Administration of transdermal patch will be at the start of IV cisplatin. For subsequent cycles, replacement of transdermal patch will start during the premedication period of IV cisplatin.

Group B: 8 mg of ondansetron orally thrice daily starting within 8 hrs of cisplatin administration and continued for 72 hours after chemotherapy infusion.

Cisplatin and premedications will be given per standard order sets and physician discretion.

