4.1 Evaluation During Study

All treatments will occur within one week time frame +/- 3 days to allow for scheduling. The patient will be given pill diaries for transdermal patch and/or Ondansetron, rescue medications, and anti-diarrheal medications. Adverse event monitoring and concomitant medications will be recorded prior to each cycle and one week after the last cycle. QOLs will be completed prior to each cycle and one week after the last cycle. Lab work and chemoradiation will be ordered at the discretion of the treating physician.

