4.2 Duration of treatment

Treatment will last 5 cycles or until the patient withdraws (Section 8.0), whichever comes first. The patient may continue to receive further chemoradiation after 5 cycles at the discretion of the treating physician; however, the patient will be taken off treatment after 5 cycles.

The transdermal patch and Ondansetron should be continued as scheduled even if the IV Cisplatin is held.

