4.3 Study Endpoints

Primary Endpoint:

1. The proportion of patients with a complete response (CR; defined as no emetic or retching episodes and no rescue medication use) during the late onset phase (4-7 days post-chemotherapy) measured during cycle 1 of chemoradiation therapy.

Secondary Endpoints:

1. The proportion of patients with a complete response (CR; defined as no emetic or retching episodes and no rescue medication use) during the acute phase (0–24 h post-chemotherapy) measured during each cycle of chemoradiation therapy.
2. The proportion of patients with a complete response (CR; defined as no emetic or retching episodes and no rescue medication use) during the delayed phase (24–72 h post-chemotherapy) measured during each cycle of chemoradiation therapy.
3. Ease of administration/compliance of two medications measured during each cycle of chemoradiation therapy.
4. Effect of nausea/vomiting on quality of life (Osoba Module – Appendix D) measured prior to each cycle of chemoradiation therapy and one week after the last cycle. Amount of nausea/vomiting in the prior week (Morrow Assessment of Nausea and Emesis (MANE Scale) – Appendix C) measured prior each cycle of chemoradiation therapy and one week after the last cycle
5. The number of dose reductions/patient during the 5 week treatment measured prior to each cycle of chemoradiation therapy.

6. The amount of “rescue medications” utilized during the 5 week treatment, including 1 week after the last cycle of cisplatin, measured during each cycle of chemoradiation therapy.

Exploratory Endpoint:

1. The amount of diarrhea experienced weekly by the patient will be graded according to CTC 4.0 and via pill counts of anti-diarrheal medication measured each cycle.

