We will use descriptive statistics to summarize the total scores for the Osoba Module, used to measure the effect of nausea and vomiting on quality of life, for each treatment group by cycle of therapy. We will compare the treatment groups with respect to the Osoba Module score with a Mann-Whitney test. We will also tabulate the responses to each of the 5 questions of the Osoba Module for each treatment group. We will also use repeated measures analysis of variance methods to model the effect of nausea and vomiting on quality of life over all cycles of therapy.

We will use descriptive statistics to summarize the number and amount of dose reductions for each treatment group for each cycle of therapy. We will also use repeated measures analysis of variance methods to model the number and amount of dose reductions over all cycles of therapy. We will similarly analyze the number and doses of rescue medications and the amount of diarrhea experienced over the course of therapy.

Technical Details

We assume a beta (1.1, 2.9) prior distribution for the treatment failure rate for each treatment. This prior distribution has a mean of 0.275 and a standard deviation of 0.200. As the trial progresses these prior distributions will be updated with the data that have accrued.

Let F_{OO} and F_{GP} be the treatment failure rates for treatments “Oral Ondansetron” (OO) and “Granisetron Patch” (GP), respectively. Prior to enrolling the 40th and subsequent patients we will calculate the randomization probability as follows. We will first calculate $\pi_{GP}(\text{data}) = \Pr(F_{GP} < F_{OO} \mid \text{data})$ and $\pi_{OO}(\text{data}) = 1 - \pi_{GP}(\text{data})$. The randomization probability for GP will then be defined as $r_{GP} = \frac{\sqrt{\pi_{GP}}}{\sqrt{\pi_{GP}} + \sqrt{\pi_{OO}}}$, and the randomization probability for OO will be $r_{OO} = 1 - r_{GP}$.

Accrual to treatment arm OO will be suspended if $\Pr(F_{OO} < 0.225 \mid \text{data}) < 0.10$. Similarly, accrual to treatment arm GP will be suspended if $\Pr(F_{GP} < 0.225 \mid \text{data}) < 0.10$. If at any point during the trial $\pi_{GP}(\text{data}) > 0.925$ (< 0.075) the trial will be terminated and treatment “Granisetron Patch” will be selected as superior (inferior). If the maximum number of patients is enrolled in the trial and $\pi_{GP}(\text{data}) > 0.915$ (< 0.085) treatment “Granisetron Patch” will be selected as superior (inferior).

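### The quality-of-life model gives the pre-cycle-1 Osoba score no role; using it as a covariate is a cheap way to gain precision, though the planned comparison is valid without it

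*Combined protocol and SAP*

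**What the plan says.** - **Schedule.** Section 4.3 has the Osoba Module "measured prior to each cycle of chemoradiation therapy and one week after the last cycle", and Section 4.1 agrees: "QOLs will be completed prior to each cycle and one week after the last cycle". Section 4.2 sets the number of cycles: "Treatment will last 5 cycles or until the patient withdraws".
- **Timing against study drug.** For cycle 1, Section 4.0 states: "Administration of transdermal patch will be at the start of IV cisplatin". Oral ondansetron in Group B is likewise tied to cisplatin. Section 3.2.4 excludes women who have already had chemotherapy. Section 4.0 repeats this and also bars those who "have received more than 7 days of radiation prior to starting their chemotherapy", so up to 7 days of radiation may precede the first form.
- **Analysis.** Section 5.0 plans descriptive summaries by cycle and tabulation of the five items. For the comparison of arms it says "We will compare the treatment groups with respect to the Osoba Module score with a Mann-Whitney test", without naming a visit. It also plans repeated measures analysis of variance methods to "model the effect of nausea and vomiting on quality of life over all cycles of therapy". It does not say whether the pre-cycle-1 score is an outcome, a covariate or unused.

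**The concern.** A score recorded before study drug cannot reflect the treatment. If it correlates with later scores, entering it as a covariate removes between-patient variation from the comparison of arms. The plan collects this score and then leaves its use open, so the longitudinal quality-of-life comparison may be less precise than the data allow.

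The stake is limited. It concerns the effect of nausea and vomiting on quality of life, which is one part of objective 1.2.4. The amount of nausea and vomiting is measured separately by the MANE. The primary endpoint, its Bayesian analysis and the sample size are not touched.

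**Working it through.** **Is there a figure to reproduce?** No. The documents give no effect size, SD, correlation or power for the Osoba Module. The sample sizes below are theirs; the correlations, SD ratios and 0.4 SD effect are assumptions.

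**1. Count of forms.** Five pre-cycle forms + 1 final form = 6. One precedes study drug and 5 follow a treated cycle.

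**2. Cost of the covariate.** Sample sizes are 75 and 150 (Section 5.0, minimum and maximum) and 97 (the Table 1 average in the design scenario, 35.4 + 61.9 = 97.3). One linear covariate with correlation rho to the outcome changes the variance of the arm difference at one visit by the factor (1 - rho²)(N - 3)/(N - 4). At rho = 0 the SE ratio is sqrt((N - 3)/(N - 4)). The covariate breaks even at rho = 1/sqrt(N - 3).

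| N | SE ratio at rho = 0 | Cost in SE | Break-even rho |
|---|---|---|---|
| 75 | sqrt(72/71) = 1.0070 | 0.7% | 0.12 |
| 97 | sqrt(94/93) = 1.0054 | 0.5% | 0.10 |
| 150 | sqrt(147/146) = 1.0034 | 0.3% | 0.08 |

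**3. Gain at a single visit, N = 97.** The net SE ratio is 1.000, 0.985, 0.959 and 0.871 at rho 0.1, 0.2, 0.3 and 0.5.

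**4. Gain for the mean of the five post-treatment forms.** Assume correlation 0.5 among those forms and a constant 0.4 SD effect.
- Unadjusted variance of a patient's mean, in SD² units: (1 + 4 × 0.5)/5 = 0.60.
- Adjusted variance: (0.60 - rho²)(N - 3)/(N - 4).
- With arms of 35.4 and 61.9, the unadjusted SE is sqrt(0.60 × (1/35.4 + 1/61.9)) = 0.163.
- Normal-approximation power at two-sided 5% is 0.688 unadjusted. Adjusted, net of the lost degree of freedom, it is as follows.

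| rho | Adjusted power (35.4/61.9) | Change in points | Range of change over the five Table 1 arm splits |
|---|---|---|---|
| 0 | 0.684 | -0.5 | -0.4 to -0.5 |
| 0.1 | 0.691 | +0.3 | +0.2 to +0.3 |
| 0.2 | 0.713 | +2.5 | about +2.5 |
| 0.3 | 0.753 | +6.5 | about +6 to +6.5 |

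At N = 75 and rho = 0 the loss is about 0.6 points.

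**5. Floored scores.** An illustrative simulation, not independently repeated, used integer scores 0-15, arms of 35 and 62, and 30% of control post-treatment scores at the floor. It compared a covariate-adjusted analysis with HC3 robust standard errors against an unadjusted unequal-variance analysis. With 90% of pre-drug scores at the floor, power was 0.579 against 0.590 at latent correlation 0, and 0.602 against 0.586 at 0.3. With 30% at the floor, it was 0.580 against 0.590 and 0.638 against 0.589. Type I error of the robust analysis was 0.041-0.052 across the settings run.

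**6. If the first form were a sixth outcome in a main-effect test.** A constant effect on five of six forms averages to 5/6 of its size. Let s be the ratio of the pre-drug SD to the later SD. The variance of the six-form mean is (s² + 5(1 + 4 × 0.5) + 10 × rho × s)/36. With arms of 35.4 and 61.9, power over rho 0 to 0.3 is 0.660-0.586 at s = 1 and 0.688-0.679 at s = 0.1, against 0.688 from the five later forms alone.

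**The case against.** The strongest reply is that nothing here is wrong. A randomised comparison of post-treatment scores is valid without a covariate, and repeated measures analysis of variance methods are a family that can include one. That stands, and the point is an improvement rather than a correction.

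The size of the benefit cannot be read from the documents. The first form precedes any cisplatin and asks about the effect of nausea and vomiting, so many women may score at the floor and the correlation may be weak. That stands too. Prior radiation of up to 7 days means that first scores need not all be alike, but it does not establish a useful correlation. The calculations also make no allowance for withdrawal or missing forms.

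A Mann-Whitney test takes no covariate, so the quoted comparison gains no precision. That is correct: the gain is confined to the repeated-measures model.

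A reader might infer that the plan dilutes the arm effect to 5/6 by averaging in a pre-drug score. The text does not support this. Six forms and five cycles leave the first form following no cycle, so an analysis over all cycles is most naturally read as the five later forms. An arm-by-time test would not be diluted in this way in any case. The dilution arises only under the less natural reading.

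**Conclusion.** The pre-cycle-1 Osoba score is collected before study drug and has no stated role in the analysis. Giving it one is a worthwhile, low-cost improvement to the longitudinal quality-of-life model.

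The downside is bounded: 0.7%, 0.5% and 0.3% in SE at 75, 97 and 150 patients, or about 0.4 to 0.6 power points over 75 patients and the Table 1 averages if the correlation is zero (about 1 point in the floored-score simulation). The upside is uncertain: a net 0.2-0.3, 2.5 and 6-6.5 points at correlation 0.1, 0.2 and 0.3, under the assumed 0.4 SD effect and 0.5 correlation among later forms. It may be near nil with heavily floored first scores. The change is therefore cheap rather than free.

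Three stronger conclusions might be drawn and are not supported: that the planned comparison is invalid, that all of objective 1.2.4 depends on this choice, or that the primary analysis is affected.

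**What to change.** Add a few sentences to the quality-of-life paragraph of Section 5.0:

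1. In the repeated-measures model, take the five post-treatment Osoba scores as outcomes and enter the pre-cycle-1 score as a single linear covariate. A covariate-by-time interaction would use up to five degrees of freedom instead of one.
2. Use robust or unequal-variance standard errors, because scores may be floored and the adaptive randomisation can make the arms unequal.
3. Have the first form completed before the patient knows her assigned arm, or use as covariate only forms completed before then. The documents do not order this form against randomisation and describe no blinding; being completed before study drug is not enough.
4. Keep the Mann-Whitney test unadjusted and name one post-treatment visit for it in advance. The form completed after cycle 1 and before cycle 2 is one option, since it matches the cycle of the primary endpoint.

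The cost is about one degree of freedom, this text, and attention to when the first form is handed out. No new instrument, visit or patient is needed.

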5.0 STATISTICAL CONSIDERATIONS

This is a randomized trial to compare oral Ondansetron (OO) and Granisetron patch (GP) for control of delayed nausea and vomiting in patients undergoing chemoradiation for the treatment of locally advanced cervical, endometrial or vaginal cancer. The primary outcome is response to anti-emetic therapy (no emetic or retching episodes and no rescue medication use) in days 4-7 of the first cycle of chemotherapy.

Patients will be randomized between OO and GP using a Bayesian adaptive algorithm. (8) Technical details of this methodology are given in the "Technical Details" section below. The first 40 patients will be randomized fairly between the 2 treatment arms. Beginning with the 41st patient and as the trial progresses and data accrue the randomization will become unbalanced in favor of the therapy that, on average, has better results in terms of treatment failure, so that each successive patient is more likely to receive the treatment showing better results.

We will enroll at least 75 and at most 150 patients at an expected rate of 5 patients per month. We will enroll up to 30 patients in LBJ. With treatment OO we expect a treatment failure rate of 0.2750. (6) With treatment GP we hope to improve the treatment failure rate to 0.1375 (i.e., reduce the treatment failure rate by half).

Beginning with the 76th patient the trial will be stopped early and a treatment selected as being "superior" if the probability is 0.925 or more that one treatment's failure rate is lower than the other treatment's failure rate. If all 150 patients are enrolled, then a treatment will be selected as being "superior" if the probability is 0.915 or more that one treatment's failure rate is lower than the other treatment's failure rate. In addition, accrual to a treatment arm will be suspended if there is less than a 0.10 chance that the treatment failure rate is less than 0.225 for that treatment arm.

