The operating characteristics of this study design are summarized in Table 1 below, and are based on 10,000 simulations of the trial for each scenario. From this table we can see that if the true treatment failure rates are 0.2750 and 0.1375 for OO and GP, respectively, then the probability that we will select GP as superior to OO is 0.799, and we expect to be able to reach this conclusion with an average of $35.4 + 61.9 = 97.3$ patients. Also, in this scenario there is only a 0.006 chance that we would select OO as superior to GP, but there is a 0.195 chance that we would conclude that neither treatment is superior to the other.

If the true treatment failure rate is 0.275 for both treatment arms, then the probability that we will select GP as superior to OO is only 0.103, and we expect to be able to reach this conclusion with an average of $48.9 + 49.2 = 98.1$ patients. Also, in this scenario there is a 0.101 chance that we would select OO as superior to GP, but there is a 0.796 chance that we would conclude that neither treatment is superior to the other.

Analysis

Once the trial is completed we will report the probability that GP has a lower treatment failure rate than OO during the late onset phase. We will also estimate the treatment failure rate for each treatment arm during the late onset phase of the first cycle of therapy with a 95% credible interval.

We will estimate with 95% confidence intervals the treatment failure rates for each treatment arm during the first 24 hours (acute phase) and during the 24-72 hour period (delayed phase) of each cycle of therapy. We will similarly estimate the treatment failure rates during the late onset phase for each cycle following cycle 1 of therapy. A treatment success is defined as no emetic or retching episodes and no rescue medication use.

We will tabulate the responses to the 4 items of the Morisky Medication Adherence (Compliance) measure for each treatment group by cycle of therapy. We will compare the 2 treatment groups with respect to the responses to each item of this instrument with a chi-square test. We will use descriptive statistics to summarize the elements of the Morrow Assessment of Nausea and Emesis (MANE Scale) and for pill counts/compliance for each treatment group by cycle of therapy. We will also use repeated measures analysis of variance methods to model compliance over all cycles of therapy.

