6.0 REGISTRATION AND RANDOMIZATION

All eligible patients will be required to provide informed signed consent before randomization and will be registered in CORe. Randomization will be performed using the Clinical Trial Conduct website (<https://biostatistics.mdanderson.org/ClinicalTrialConduct>), which is maintained by the Department of Biostatistics. Research personnel responsible for enrolling and randomizing patients on this trial will be trained by the study statistician in the use of the website, with particular attention to the importance of updating patient outcomes. Access to the website is gained through usernames and passwords.

Table 1. Operating Characteristics of Study Design			
	Neither	Oral Ondansetron	Granisetron Patch
True Probability of Failure	---	0.2750	0.1375
# Patients Treated Avg (2.5%-tile, 97.5%-tile)	---	35.4 (21, 67)	61.9 (39, 102)
Pr(Selected)	0.1950	0.0060	0.7990
Pr(Selected Early)	---	0.0060	0.7740
Avg Trial Duration		19.6 months	
True Probability of Failure	---	0.2750	0.1750
# Patients Treated Avg (2.5%-tile, 97.5%-tile)	---	42.4 (22, 75)	64.0 (34, 101)
Pr(Selected)	0.4266	0.0154	0.5620
Pr(Selected Early)	---	0.0149	0.5340
Avg Trial Duration		21.6 months	
True Probability of Failure	---	0.2750	0.2250
# Patients Treated Avg (2.5%-tile, 97.5%-tile)	---	48.1 (24, 83)	59.0 (29, 97)
Pr(Selected)	0.6783	0.0487	0.2730
Pr(Selected Early)	---	0.0454	0.2520
Avg Trial Duration		21.7 months	
True Probability of Failure	---	0.2750	0.2750
# Patients Treated Avg (2.5%-tile, 97.5%-tile)	---	48.9 (26, 88)	49.2 (25, 88)
Pr(Selected)	0.7960	0.1010	0.1030
Pr(Selected Early)	---	0.0093	0.0927
Avg Trial Duration		19.8 months	
True Probability of Failure	---	0.2750	0.3250
# Patients Treated Avg (2.5%-tile, 97.5%-tile)	---	47.9 (28, 88)	40.1 (23, 76)
Pr(Selected)	0.7757	0.1910	0.0333
Pr(Selected Early)	---	0.1730	0.0298
Avg Trial Duration		17.7 months	

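### Technical Details drops the 75-patient minimum from the 0.925 superiority stop; followed as written, it would raise false selection of an arm 1.4 to 2.9 times

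*Combined protocol and SAP*

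**What the plan says.** Section 5.0 gives the early superiority rule twice.

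- **Main text.** "We will enroll at least 75 and at most 150 patients", and "Beginning with the 76th patient the trial will be stopped early and a treatment selected" as superior when the posterior probability that one failure rate is below the other is at least 0.925. At 150 patients the threshold is 0.915.
- **Technical Details.** "If at any point during the trial" π_GP exceeds 0.925 or falls below 0.075, the trial ends and the granisetron patch (GP) is declared superior or inferior to oral ondansetron (OO). There is no minimum, no starting patient and no reference back to the 76th.

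The main text introduces the adaptive algorithm and points onward: "Technical details of this methodology are given in the" Technical Details subsection. The operating characteristics "are based on 10,000 simulations of the trial for each scenario" and appear in Section 6.0 under "Table 1. Operating Characteristics of Study Design". Section 6.0 also says "Randomization will be performed using the Clinical Trial Conduct website", without saying which statement of the rule the site was set up from.

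There is a smaller mismatch on the start of adaptive allocation. The main text has "Beginning with the 41st patient and as the trial progresses"; Technical Details calculates the allocation probability from the 40th patient.

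**The concern.** A trial cannot both enrol at least 75 patients and terminate whenever the threshold is crossed. The Technical Details sentence can be read as allowing looks from the first patient, or from about patient 40, where that subsection first calculates π_GP. Neither reading keeps the minimum.

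This is the rule that declares a treatment superior. A 0.925 posterior threshold is easily crossed by chance when data are few and looks are frequent, so the minimum does much of the work of holding down false selection. If the sentence without it were operated, the stated error rates and sample sizes would no longer describe the trial.

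**Working it through.** **Inputs, all from Section 5.0.** Beta(1.1, 2.9) prior on each arm's failure rate; first 40 patients randomized equally (simulated as 20 per arm); maximum 150; early threshold 0.925, final threshold 0.915; an arm is suspended if Pr(F < 0.225 | data) < 0.10.

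**Formulas.** With x failures among n patients, an arm's posterior is Beta(1.1 + x, 2.9 + n − x). π_GP = Pr(F_GP < F_OO | data), and the allocation probability is r_GP = √π_GP / (√π_GP + √π_OO).

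**Assumptions.** A look after every patient, outcomes known at once, 40,000 simulated trials per cell. The plan does not say when suspension checks begin or what suspension does to the trial as a whole, so three readings were run:

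- A: the trial ends without selection once either arm meets the suspension rule, checked from 75 outcomes.
- B: only that arm is suspended, checked from 75 outcomes; the trial ends if both are.
- C: as B, but checked from the start.

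**Step 1: the plan's own figures.** Under the null (0.275 in both arms), Table 1 gives 0.101 + 0.103 = 0.204 for selecting either arm, and 48.9 + 49.2 = 98.1 patients on average. Under the design alternative (0.275 v 0.1375) it gives 0.006 + 0.799 = 0.805 and 35.4 + 61.9 = 97.3 patients.

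**Step 2: which rule produced Table 1?** Reading A is the closest match. OO failure rate is 0.275 throughout.

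| GP failure rate | 0.1375 | 0.175 | 0.225 | 0.275 | 0.325 |
|---|---|---|---|---|---|
| Either arm selected, Table 1 | 0.805 | 0.577 | 0.322 | 0.204 | 0.224 |
| Minimum 75 | 0.805 | 0.572 | 0.300 | 0.183 | 0.207 |
| Looks from patient 1 | 0.879 | 0.742 | 0.587 | 0.526 | 0.556 |
| Mean N, Table 1 | 97 | 106 | 107 | 98 | 88 |
| Minimum 75 | 94 | 103 | 106 | 98 | 87 |
| Looks from patient 40 | 72 | 84 | 90 | 85 | 75 |
| Looks from patient 1 | 53 | 64 | 69 | 65 | 56 |

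The match with the minimum is close but not exact: selection is about 0.02 low in three rows. Across all three suspension readings, looks from patient 1 give mean sizes of 44-75 in the five rows, against 88-107 in Table 1. Table 1 therefore describes the 76th-patient rule.

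**Step 3: null selection of either arm, by first look.**

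| Suspension reading | From 75 | From 40 | From 1 | Ratio 40/75 | Ratio 1/75 |
|---|---|---|---|---|---|
| A | 0.183 | 0.358 | 0.526 | 1.96 | 2.87 |
| B | 0.305 | 0.423 | 0.577 | 1.39 | 1.89 |
| C | 0.233 | 0.357 | 0.535 | 1.53 | 2.30 |

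Runs of 10,000 trials with the first look at 39 or 41 stay within 0.35-0.43, so the 40th/41st mismatch has negligible effect. An arm is selected before 75 patients in 0.30-0.33 of null trials (from 40) and 0.49-0.50 (from 1).

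**Step 4: design alternative.** Ranges are over the three readings.

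| | Table 1 | From 75 | From 40 | From 1 |
|---|---|---|---|---|
| Wrong selection of OO | 0.006 | 0.004-0.013 | 0.012-0.024 | 0.044-0.055 |
| Mean N | 97.3 | 89-95 | 66-72 | 49-54 |

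**Step 5: how early the literal rule can fire.** With 2 failures in 2 on OO and 0 in 3 on GP, the posteriors are Beta(3.1, 2.9) and Beta(1.1, 5.9). Numerical integration gives π_GP = 0.937, above 0.925 after 5 patients.

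**Step 6: fewer looks or delayed outcomes** (smaller runs, null, suspension from 75; first look 75 / 40 / 1).

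- Every 5 patients: 0.178 / 0.300 / 0.402 (as A) and 0.281 / 0.373 / 0.462 (as B).
- Every 10 patients: 0.171 / 0.267 / 0.374 (as A) and 0.264 / 0.349 / 0.437 (as B).
- Every patient, outcomes lagging by 6 patients (as B): 0.328 / 0.452 / 0.589.

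The absolute values move, but dropping the minimum raises false selection each time.

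**The case against.** The strongest reply is that the documents settle the matter themselves. The main text states the minimum twice, Table 1 fits only that rule, and Technical Details may simply have left out a qualifier given earlier in the section. On that view the stated operating characteristics are sound and the harm is hypothetical, since nothing suggests the website was set up without the minimum. The pointer to Technical Details is attached to the allocation algorithm and does not make that subsection override the stopping rule.

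Much of this stands. The intent is clear, and the inflation is conditional on the wrong sentence being operated. The patient-1 figures are a literal worst case, because the plan describes no calculation of π_GP before about patient 40. Measuring the rise from 0.204 would also mix baselines: like for like, the patient-40 increase is 0.12 to 0.18. Fewer looks shrink the figures, and reading A ends the trial in a way the text does not state.

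None of this reconciles the two sentences. The faulty one sits beside the formulas that a programmer would implement, it is worded as a complete rule, and following it gives the wrong design.

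**Conclusion.** The concern holds. The plan contains two incompatible rules for declaring superiority, and only the one starting at the 76th patient agrees with its published operating characteristics. If the Technical Details sentence were operated with a look after every patient, null selection of either arm would be 0.35-0.43 (looks from about patient 40) or 0.53-0.58 (looks from patient 1), against 0.18-0.31 with the minimum and 0.204 in Table 1.

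These sizes are approximate. They rest on immediate outcomes and on three readings of an incompletely specified suspension rule, none of which reproduces Table 1 exactly. The direction does not depend on those choices. Because the sentence governs the trial's primary conclusion, it must be corrected.

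**What to change.** In Technical Details, replace the opening of the early-termination sentence with a start at the 76th patient, once at least 75 are enrolled, so that it agrees with the main text and Table 1. Confirm, and record, that the randomization website applies the 0.925 rule only from that point. While editing, use the 41st patient in both places for the start of adaptive allocation.

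The cost is one sentence of protocol wording and a settings check. Table 1 already reflects the intended rule and need not be rerun for this change.
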